4.3.3 Masking Procedures

Due to the staggered, dose-escalation design of the trial, it will not be possible to blind to *Na-APR-1* (M74)/Alhydrogel® or *Na-GST-1*/Alhydrogel® dose assignment. That is, those subjects enrolled into Groups 1 and 2 will receive either 10µg *Na-APR-1* (M74)/Alhydrogel® administered to one arm and 10µg *Na-GST-1*/Alhydrogel® administered to the alternate arm, or the hepatitis B vaccine in one arm and sterile saline administered to the alternate arm. Subjects enrolled into Groups 3 and 4 will receive either 30µg *Na-APR-1* (M74)/Alhydrogel® administered to one arm and 30µg *Na-GST-1*/Alhydrogel® administered to the alternate arm, or the hepatitis B vaccine in one arm and sterile saline administered to the alternate arm, and so on.

Investigators and subjects will be blinded to the within-Group random allocation to receive co-administered *Na-APR-1* (M74)/Alhydrogel® and *Na-GST-1*/Alhydrogel® or co-administered hepatitis B vaccine and sterile saline until all subjects have completed their Day 208 visit, the safety and secondary immunogenicity outcomes (i.e., anti-*Na-GST-1* and anti-*Na-APR-1* [M74] IgG antibody results by ELISA) have been monitored and entered into the database, and the database has been “soft-locked” for interim analysis. Procedures to maintain blinding include administering two injections to all subjects at each vaccination point. For this, sterile saline will be co-administered to those subjects randomized to receive the hepatitis B vaccine.

The study vaccine manager and his assistant will prepare all investigational product doses (vaccine or sterile saline placebo) in a separate room, and will hand filled syringes to the vaccinator(s). Since the 10 and 30µg doses of the *Na-APR-1* (M74) and *Na-GST-1* formulations are of different volumes than that of hepatitis B vaccine, the contents of all syringes will be disguised using opaque tape. As a further precaution, the vaccinator(s) will not be involved in assessments of reactogenicity or adverse events.

Investigators will be unblinded after all subjects have had their study Day 208 visit (i.e., 1 month after the final vaccination for those children randomized to receive vaccines on the 0, 2, and 6-month schedule), the safety and secondary immunogenicity outcomes (i.e., anti-Na-GST-1 and anti-Na-APR-1 (M74) IgG antibody results by ELISA) have been monitored and entered into the database, and the database has been “soft-locked” for interim analysis. After this point, the study will be single-blinded (i.e., subjects will remain blinded to what products they received). The principal justification for unblinding the investigators before the final study visit has been completed is that the safety and immunogenicity data acquired during the vaccination phase of the study will be crucial in guiding the human hookworm vaccine clinical development plan, and we feel that to make an informed decision as to whether or not to proceed to pediatric trials, we must first assess the unblinded data in a timely fashion.

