2.2 Study Outcome Measures

2.2.1 Primary Outcome Measures

Safety

The following parameters will be evaluated for each dose of *Na-APR-1* (M74) co-administered with *Na-GST-1*:

1. Frequency of solicited injection site and systemic reactogenicity, graded by severity, on the day of each study vaccination through 14 days after each study vaccination.
2. Frequency of study vaccine-related serious adverse events from the time of the first study vaccination through approximately 9 months after the last study vaccination.
3. Frequency of clinical safety laboratory adverse events.
4. Frequency of unsolicited adverse events, graded by severity, from the time of each study vaccination through approximately 1 month after each study vaccination.
5. Frequency of new-onset chronic medical conditions through approximately 9 months after the third study vaccination.
6. Frequency of Adverse Events of Special Interest through approximately 9 months after the third study vaccination.

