3 STUDY DESIGN

The study will be conducted as a randomized, placebo-controlled, double-blind Phase 1 dose-escalating clinical trial in healthy children between the ages of 6 and 10 years, inclusive, living in the hookworm-endemic area of Lambaréné, Gabon. The study is designed to evaluate the safety, reactogenicity, and immunogenicity of Na-GST-1/Alhydrogel® co-administered with Na-APR-1 (M74)/Alhydrogel®, as compared to the hepatitis B vaccine, in this age group.

Prior to beginning study-related activities, the consent and cooperation of representative community members will be sought, after which parents of potential pediatric participants will be invited to learn about the study and consent to the participation of their child. After a parent or legal representative provides written informed consent for the child's participation and passes the informed consent comprehension questionnaire, the child will undergo eligibility screening, including a complete medical history, physical examination, hematology testing, liver and renal function testing, HIV antibody testing, Hepatitis B and C serology, and urinalysis. In addition, a fecal examination will be performed for ova and parasites, and urine will be examined for *S. haematobium* ova. All clinically significant abnormalities will be reviewed with parents/legal guardians and referral of the child for follow-up care will be provided. After screening, those children determined to be eligible, based on the inclusion and exclusion criteria, will be invited to participate in the study.

Sixty children will be progressively enrolled into 1 of 3 Groups over a projected 3-month enrollment period, with each child followed for 9 months after the final injection (i.e., until Study Day 380 for those receiving vaccinations according to a 0,2,4-month schedule and until Study Day 448 for those receiving vaccinations according to a 0,2,6-month schedule). Group enrollment will be done in an open sequential fashion, whereas within each Group, investigational product (IP) assignment and vaccination will be done in a randomized double-blind fashion.

60 subjects will be enrolled into 3 groups of 20:

The first 20 subjects will be recruited and enrolled into Group 1:

- Group 1 double-blind IP allocation (n=20):
 - 16 subjects will receive 10µg Na-APR-1 (M74) plus 5µg GLA-AF delivered by IM injection in the deltoid muscle, with 10µg Na-GST-1 administered IM in the alternate arm.

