The study will be double-blinded until all study subjects have completed their Day 208 visit, the safety and secondary immunogenicity outcomes (i.e., anti-Na-GST-1 and anti-Na-APR-1 (M74) IgG antibody results by ELISA) have been monitored and entered into the database, and the database has been “soft-locked” for interim analysis. After this milestone, the Sponsor and investigators will be unblinded. During the double-blinded part of the study, a study subject’s randomization code may be unblinded only for safety purposes. This is unlikely to occur, since once a vaccine is administered, knowing which vaccine was given is unlikely to influence the medical management of an AE. This procedure is therefore exceptional and any decision to unblind will be discussed with the sponsor, the Principal Investigator, the Independent Medical Monitor, and the SMC. If deemed necessary for urgent safety reasons, the Independent Medical Monitor, in consultation with the SMC (if possible in a timely manner), may unblind a specific subject without revealing the study blind to the investigators or the Sponsor. Any unblinding will be thoroughly documented. It is to be emphasized that the Independent Medical Monitor may put the study on hold at any time and discuss with the SMC. In the event that the investigators come to know the study code prior to final unblinding, the Principal Investigator must notify the Sponsor immediately. The reasons will be documented by the Principal Investigator and added to the study file.

The decision to completely unblind the study prior to Day 208 or permanently stop the study prior to the final study visit of all participating children will take the form of a formal recommendation by the SMC to the study Sponsor. The Principal Investigator must then notify the IRB of this decision.

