14.4 Timing/Reports

In addition to the study-related documentation required by the regulatory authorities, 4 study reports will be generated. These include 2 interim SMC safety reports, 1 interim safety and immunogenicity study report, and the final study report. The first interim SMC safety report will be completed after the safety data from the Day 14 visits of Group 1 have been compiled, for the purposes of deciding whether it is safe to proceed with enrollment into Group 2 of the study. The

second interim SMC safety report will be completed after the safety data from the Day 14 visits of Group 2 have been compiled, for the purposes of deciding whether it is safe to proceed with enrollment into Group 3 of the study. The interim study report will be compiled after interim safety and primary immunogenicity data (i.e., antigen-specific IgG responses to Na-GST-1 and Na-APR-1 (M74) as determined by ELISA) from all Day 208 visits is available and the study investigators unblinded. This report will serve as the basis for deciding whether to continue with future Phase 2 testing of the vaccines in children. A final report containing all safety and immunology data will be prepared after trial completion.

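### Investigators learn individual allocations at the post-Day 208 soft lock, while three of six primary safety outcomes that rest partly on their judgement run on to Day 380/448

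*Combined protocol and SAP*

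**What the plan says.** **Trigger.** Protocol Section 4.3.3 (Masking Procedures): "Investigators will be unblinded after all subjects have had their study Day 208 visit". The visit is not enough by itself. The safety and IgG ELISA outcomes must also "have been monitored and entered into the database, and the database has been" soft-locked for the interim analysis.

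**Who is told.** Section 8.5 (Halting Rules) includes the sponsor: "After this milestone, the Sponsor and investigators will be unblinded". Section 4.3.3 describes what follows: "After this point, the study will be single-blinded (i.e., subjects will remain blinded to what products they received".

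**What is still being measured.** Section 2.2.1 lists six primary safety outcomes. One is "Frequency of study vaccine-related serious adverse events from the time of the first study vaccination through approximately 9 months after the last study vaccination". New-onset chronic medical conditions and AESIs have the same horizon. Section 3 (Study Design) follows children "until Study Day 380 for those receiving vaccinations according to a 0,2,4-month schedule and until Study Day 448" for the 0,2,6-month schedule.

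**Who judges.** Section 8.2.1 has the investigator grade AE severity, and every AE is also assessed for relationship to vaccine. Section 4.3.3 keeps the vaccinators out of AE assessment, and Section 4.3.1 does the same for the vaccine manager and assistant. Neither section provides for blinded assessment after the investigators are unblinded.

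**Why.** Section 4.3.3 says that unblinded data are needed "to make an informed decision as to whether or not to proceed to pediatric trials". Section 14.4 gives the interim report a different purpose: "This report will serve as the basis for deciding whether to continue with future Phase 2 testing of the vaccines in children".

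**The concern.** For one late outcome, the judgement is part of the definition: an SAE counts only if it is called vaccine-related. For AESIs and new chronic conditions, what is open to influence is ascertainment, that is, how hard a complaint is pursued and whether it is given a listed diagnosis. Section 8.3.3 explains that AESIs are watched because an immunostimulatory adjuvant might cause them, and only the hookworm arm receives GLA-AF. An assessor who knows a child's allocation therefore knows whether that child had the adjuvant under suspicion. The resulting bias could go in either direction.

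The numbers are small, so a single decision shows. One event attributed differently moves a dose group's hookworm rate by 1/16 = 6.25 percentage points, or the pooled comparator rate by 1/12 = 8.3 points.

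The reason given for unblinding also does not fit. It refers to a decision on whether to begin paediatric trials, but this is a paediatric trial.

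**Working it through.** **1. Which primary outcomes are still open at unblinding?** The windows come from Sections 2.2.1 and 8.1.

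| Primary outcome | Window | Open after unblinding? |
|---|---|---|
| Solicited reactions | 14 days after each dose | No |
| Safety laboratory AEs | about 14 days after each dose | No |
| Unsolicited AEs | about 28 days after each dose (nominal Day 140/208) | No |
| Vaccine-related SAEs | about 9 months after last dose | Yes |
| New-onset chronic conditions | about 9 months after dose 3 | Yes |
| AESIs | about 9 months after dose 3 | Yes |

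Three of six remain open.

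**2. End of follow-up.** Dose 3 is on Day 112 or 180. Adding 9 months (274 days) gives Day 386 or 454. The stated Days 380 and 448 are 268 days after dose 3, a difference that lies inside the ±21-day visit window. The stated days are used below.

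**3. Person-time after unblinding.** The documents give no figure for this share.

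Inputs:
- Follow-up of 380 or 448 days (Section 3).
- Ten children per group on each schedule (Section 4.3.2), so the six group-by-schedule cells carry equal weight.
- Enrolment projected at 3 months (Section 3), taken as Groups 1, 2 and 3 starting on calendar days 0, 45 and 90. The even spacing is an assumption.
- Lag L from the last Day 208 visit to soft lock. No duration is stated, so L is varied.

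Unblinding falls on calendar day 90 + 208 + L = 298 + L. Days left in a cell = start day + 380 (or 448) − (298 + L), set to zero if negative.

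| Cell | Days left, L = 0 | Share of own follow-up |
|---|---|---|
| 1A | 0 + 380 − 298 = 82 | 21.6% |
| 1B | 0 + 448 − 298 = 150 | 33.5% |
| 2A | 45 + 380 − 298 = 127 | 33.4% |
| 2B | 45 + 448 − 298 = 195 | 43.5% |
| 3A | 90 + 380 − 298 = 172 | 45.3% |
| 3B | 90 + 448 − 298 = 240 | 53.6% |
| Sum | 966 of 3 × (380 + 448) = 2,484 | 38.9% |

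Effect of the lag:
- L = 30: (966 − 6 × 30)/2,484 = 786/2,484 = 31.6%.
- L = 60: (966 − 6 × 60)/2,484 = 606/2,484 = 24.4%.
- L = 90: cell 1A has finished, and the other five leave 60 + 37 + 105 + 82 + 150 = 434; 434/2,484 = 17.5%. Spreading entry evenly child by child gives 17.3%.

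Effect of enrolment speed at L = 0: a 120-day stagger gives 35.3% and a 180-day stagger about 28%. With no stagger at all the share would be (172 + 240)/(380 + 448) = 49.8%, an arithmetic limit that the sequential design rules out.

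**4. Does the stated purpose need unblinded assessors?** Section 14.1 gives analysis and reporting to the data management vendor. Section 8.6.2 already gives the SMC and the Independent Medical Monitor access to the code. Section 8.5 itself says that knowing the vaccine is unlikely to change how an AE is managed. The development decision needs results by arm; it does not need site staff to know who received what.

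**The case against.** The strongest reply is that this choice is disclosed and reasoned, in a Phase 1 trial that Section 10.1 says is not powered for group differences. Several parts of that reply stand.

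- **The size is easily overstated.** A reader might take about 40% as the expected share. It is not, because the trigger also needs ELISA results and a soft lock. The assays are run in Washington (Section 7.2.2) on samples shipped in batches (Section 7.2.3.2), so zero lag is unlikely and any lag lowers the share. Faster enrolment would raise it, but only so far. Section 8.6.2 asks for 14-day data on the whole preceding group and an SMC call at least a week before the next, about 21 days per step or 42 in all. The same formula then gives 1,110/2,484 = 44.7%, still at zero lag and well short of the projected 3 months.
- **Person-time is not the share of assessments.** Appendix A lists 21 visits per child from Day 0, or 126 over the six cells. At zero lag and the 90-day stagger, 13 of these (10.3%) fall after unblinding. Events may be reported between visits, so person-time remains relevant.
- **Not every late outcome is equally soft.** AESIs are named diagnoses counted whatever their relatedness, and the seriousness criteria are largely objective. The exposure lies mainly in SAE relatedness and in ascertainment.
- **Dose comparisons lose nothing.** Section 4.3.3 says that dose cannot be blinded, so only the 48 versus 12 hookworm versus hepatitis B comparison is affected.

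Disclosure does not settle the matter, because the reason disclosed can be met without unblinding the assessors. Low power does not settle it either: the primary aim is to estimate event frequencies, and biased attribution distorts an estimate whatever the power.

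**Conclusion.** The concern holds within limits. Three of six primary safety outcomes are partly assessed by investigators who know individual allocations, with no blinded assessment described. The affected share is up to about 39% of planned person-time at the projected 3-month enrolment with zero lag, and about 17% to 32% if the soft lock takes an assumed 1 to 3 months. The lag is the main unknown, since the documents give no duration.

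A reader might infer that the primary safety analysis as a whole is compromised, or that the dose-escalation findings are. The documents support neither: the acute reactogenicity, laboratory and 28-day windows nominally close while investigators are still blinded, and dose was never masked. Nor do they show that bias will occur; they show only that an avoidable opening for it is left in the late hookworm versus hepatitis B comparison. The paediatric-trials rationale is a separate inconsistency to reconcile and is not evidence of bias.

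**What to change.** Amend Sections 4.3.3, 8.5 and 14.4 as follows.

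1. At soft lock, unblind only the sponsor's decision-makers and the reporting statistician at the data management vendor. Pool the interim tables enough that the two comparator children in each schedule cell cannot be recognised.
2. Withhold individual allocations and individual IgG results, which could reveal allocation, from site staff who detect, grade or attribute events until the last Day 448 visit and final lock.
3. Keep the existing route through the SMC and the Independent Medical Monitor for safety unblinding.
4. Reconcile the rationale in Section 4.3.3 with the Phase 2 decision in Section 14.4.

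Cost: the wording of three sections and care in laying out the interim tables. Site investigators wait longer for individual allocations and antibody results, by up to 448 − 208 = 240 days (about 8 months) from the last Day 208 visit to the last Day 448 visit, plus the time to final lock. No visits or staff are added, since the existing site team simply stays blinded, and the Phase 2 decision need not be delayed.

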4.3.4 Reasons for Withdrawal and Discontinuation of Vaccinations

Parents/guardians will be free to withdraw their child from the study at any time and for any reason, without penalty. Children who have received vaccine, regardless of the number of doses received, or who developed an AE or SAE will be strongly encouraged to remain in the study to be followed for safety purposes.

A child may withdraw or be withdrawn from the study for any of the following reasons:

- Withdrawal of consent of the parent or legal guardian.
- Withdrawal of assent of the child.
- As deemed necessary by the Principal Investigator or appropriate co-investigator for noncompliance or other reasons.
- Subject lost to follow-up.
- Early termination of the study.

The second or third study vaccination may not be administered to a child if any of the following criteria are met (although the child will remain in the study for safety follow-up visits):

- Medical condition for which continued participation, in the opinion of the Principal Investigator or appropriate co-investigator, would pose a risk to the child or would be likely to confound interpretation of the results.
- Presence of signs or symptoms that could confound or confuse assessment of study vaccine reactogenicity. For children with injection site or systemic signs or symptoms, or with an acute illness, including a tympanic temperature greater than 38.0°C, the study vaccination should/may be postponed/deferred until signs, symptoms, or acute illness have resolved and if within the acceptable protocol-specified window for that visit. If outside this window, the Sponsor must first approve the second or third study vaccination and the documentation of approval should be filed in the child's chart.

- Any unresolved or continuing solicited or unsolicited Grade 3 adverse event. An unresolved or continuing Grade 1 or Grade 2 adverse event is permissible unless, in the opinion of the Principal Investigator or appropriate co-investigator, it would render study vaccination unsafe or interfere with the evaluation of responses.
- Grade 3 clinical safety laboratory value that does not decrease to Grade 2 or less prior to the second or third study vaccination. Any clinical safety laboratory parameter may be re-evaluated only once at the clinical laboratory prior to the second or third study vaccination. If the clinical safety laboratory value decreases to Grade 2 or less, the child may receive the second or third study vaccination. The second or third study vaccination should be scheduled to occur within the acceptable protocol-specified window for that visit. If outside this window, the Sponsor must first approve the study vaccination and the documentation of approval should be filed in the child's chart.
- Severe or sustained reaction or disability related to the first study vaccination.
- New onset of illness or condition that meets exclusion criteria.
- Child no longer meets eligibility criteria.
- As deemed necessary by the Principal Investigator or appropriate co-investigator for noncompliance or other reasons.
- Refusal of further study vaccination by the parent/guardian.
- Withdrawal of consent of the parent or legal guardian.
- Child lost to follow-up.
- Early termination of the study.
- New information becomes available that makes further vaccinations unsafe.

